12.3. SUSARs

If the event is evaluated as a Suspected Unexpected Serious Adverse Reaction (SUSAR), UCL CTC will submit a report to the MHRA within the required timelines.

Wherever possible, evaluations of causal relationship by both the site and the Sponsor's clinical reviewer will be reported.

UCL CTC will submit all SUSAR reports relating to nivolumab to Bristol-Myers Squibb (BMS) according to the timelines outlined in the agreement between UCL and BMS.

Informing Sites of SUSARs

UCL CTC will inform all PIs of any SUSARs that occur on the trial. PIs will receive a quarterly line listing which must be processed according to local requirements.

12.4. Adverse events of special interest

All AESIs must be submitted to UCL CTC by fax or email within the timeframes outlined below, using the trial specific SAE Report. All sections on the SAE Report must be completed. If the event is **not being reported within the required timeframe** to UCL CTC, the circumstances that led to this must be detailed in the SAE Report to avoid unnecessary queries.

UCL CTC will submit all SAE Reports relating to AESIs in patients who have received Nivolumab to BMS according to the timelines outlined in the agreement between UCL and BMS.

12.4.1. Autoimmune events due to Nivolumab

The following adverse events of special interest for Nivolumab must be reported on the appropriate AE of Special Interest form within **24 hours of confirmed diagnosis.**

The following adverse events of special interest for Nivolumab must be reported on an SAE report form within **24 hours of confirmed diagnosis.** Please note that any signs and symptoms should be treated on their merits and reported as AEs/SAEs as applicable pending confirmation of diagnosis.

To summarise, the reporting requirements for **autoimmune events** based the treatment arm are as follows: (please note that the reporting window for autoimmune events differs to those for non-autoimmune SAEs; see section 12.2.2 for details).

Next Treatment	Reporting window for autoimmune toxicity
No treatment or further chemotherapy	From first administration of nivoumab until 5 months post last dose of trial treatment (or after this date if the investigator feels the event is related to nivolumab).
Autologous stem cell transplant	From first administration of nivoumab until 5 months post last dose of trial treatment (or after this date if the investigator feels the event is related to nivolumab).
Allogeneic stem cell transplant	From first administration of nivoumab until 5 months post last dose of trial treatment (or after this date if the investigator feels the event is related to nivolumab).
	Please note that colitis, dermatitis and hepatitis occurring after transplant day 0 should be reported as graft-versus-host disease in the first instance unless otherwise proven to be of autoimmune origin (see section 12.5 (Urgent Events) for details of reporting graft-versus-host disease).

Please note that confirmed autoimmune events must be reported to the CTC on an SAE report form even if the patient has received further treatment for their lymphoma within the 5 months after completing nivolumab.

Events will be collected as follows:

Event	Description See section 8.5 for detailed definitions	Form required	Timeframe
Autoimmune diarrhoea / colitis	Grade ≥2 diarrhoea persisting >48 hours and not suspected clinically or confirmed on lab testing to be due to infective causes	SAE report	Within 24 hours of confirmed diagnosis
Autoimmune uveitis	New or worsening inflammation of the eye, with ocular pain, erythema or blurring of vision.	SAE report	Within 24 hours of confirmed diagnosis
Autoimmune pneumonitis	Radiographic changes or pulmonary symptoms, unless due to infective causes	SAE report	Within 24 hours of confirmed diagnosis
Autoimmune hepatitis	Raised ALT, AST or bilirubin, unless due to infective causes or other concomitant medications	SAE report	Within 24 hours of confirmed diagnosis
Autoimmune dermatitis	New or worsening rash where non-autoimmune causes have been excluded	SAE report	Within 24 hours of confirmed diagnosis
Immune related endocrinopathy	New or worsening asymptomatic or symptomatic endocrine disfunction	SAE report	Within 24 hours of confirmed diagnosis

Autoimmune renal toxicity	Raised creatinine unless due to nephrotoxicity of concomitant medications or outflow tract obstruction	SAE report	Within 24 hours of confirmed diagnosis
Autoimmune neurological toxicity	New or worsening radiographic changes or neurological symptoms	SAE report	Within 24 hours of confirmed diagnosis

Cases of autoimmune toxicity must be reported on the trial-specific SAE report by fax or email:

[contact]

Email: [contact]

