8.5.1.3 Management of autoimmune hepatitis

Exclude infective and disease related causes, and hepatotoxicity of other concomitant medications

Hepatitis CTCAE v5 grade	Action – trial treatment	Recommended management of toxicity
Grade 1: AST or ALT >ULN - 3xULN and/or Bilirubin >ULN - 1.5xULN	Continue nivolumab treatment at 240mg.	Continue monitoring of liver function tests as per protocol. If worsening, treat as G2 or G3-4
Grade 2: AST/ALT >3xULN - 5xULN and/or	Delay nivolumab treatment	Increase frequency of monitoring to every 3 days If persists >3 days or worsens:

Bilirubin >1.5xULN - 3xULN	Restart nivolumab at 240mg if/when results improve to baseline. If steroids given, patient must have been weaned to ≤10mg per day (or equivalent) before restarting treatment. Maximum permitted delay 4 weeks.	Steroid treatment as per local policy (recommended dose 0.5-1mg/kg/day IV methylprednisolone or equivalent dose of any oral steroids). If no improvement after a further 3 days, treat as for G3-4. Consider prophylactic antibiotics for opportunistic infections.
Grade 3-4: AST or ALT >5xULN and /or Bilirubin >3xULN	Permanently discontinue nivolumab treatment.	Increase frequency of monitoring to every 1-2 days: Steroid treatment as per local policy (recommended dose 1-2mg/kg/day IV methylprednisolone or equivalent dose of oral steroids). Add prophylactic antibiotics for
		opportunistic infections. Consult gastroenterologist.
		If returns to G2:
		taper steroids over at least 4 weeks
		If not improving after 3-5 days or rebounds:
		give additional immunosuppression as per local policy.

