8.5.1.4 Management of autoimmune dermatitis

New or worsening rash. Exclude other non-autoimmune causes e.g. swab potentially infective lesions.

Rash CTCAE v5 grade	Action – trial treatment	Recommended management of toxicity
Grade 1-2:	Continue nivolumab treatment at	Treat symptoms as per local
G1: Rash covers <10% body	240mg.	policiese.g. anti-histamines, topical steroids
surface area	If persists >1-2 weeks despite	•
G2: Rash covers 10-30% body surface area	symptomatic treatment or recurs:	If persists >1-2 weeks or recurs:
	Delay nivolumab treatment	Consider skin biopsy.
	Restart nivolumab at 240mg if/when symptoms improve If steroids given, patient must have been weaned to ≤10mg per	Consider steroid treatment as per local policy (recommended dose 0.5mg to 1mg/kg/day IV

Grade 3: Covering >30% body surface area; erythroderma Grade 4: Life-threatening consequences	day (or equivalent) before restarting treatment. Maximum permitted delay 4 weeks. For grade 3: Delay nivolumab treatment. Restart nivolumab at 240mg if/when symptoms resolve. If steroids given, patient must have been weaned to ≤10mg per day (or equivalent) before restarting treatment. Maximum permitted delay 4 weeks. For grade 4: Permanently discontinue nivolumab treatment.	methylprednisolone equivalent dose of oral steroids). If worsens: treat as G3-4. Consider skin biopsy. Dermatology referral recommended. Steroid treatment as per local policy (recommended dose 1-2mg/kg/day IV methylprednisolone or equivalent dose of oral steroids). Prophylactic antibiotics against opportunistic infections.
Stevens-Johnson syndrome (SJS) or toxic epidermal necrolysis (TEN)	Permanently discontinue treatment.	Refer to specialist unit for assessment and treatment.

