12.2.1. Reporting of Adverse Events (AEs)

All adverse events that occur between the start of nivolumab treatment and 3 months post last nivolumab administration or commencement of next treatment for lymphoma (whichever is earlier) must be recorded in the the trial CRFs.

The reporting period has been selected as the patients are followed up at 1, 2, 3 months, then moving to 3 monthly follow up schedule. It is anticipated that most patients will have proceeded to further lymphoma treatment by the 3 month timepoint.

Adverse events meeting the definition of a Serious Adverse Event (SAE) or Adverse Event of Special Interest (AESI) must also be reported to UCL CTC using the trial specific SAE Report. Also refer to section 12.2.2 (Reporting of Serious Adverse Events (SAEs)) and section 12.4 (Adverse Events of Special Interest). Adverse events meeting the definition of an Urgent Event must also be reported on an Urgent Event form (also refer to section 12.5 Urgent Events).

Pre-existing conditions do not qualify as adverse events unless they worsen.

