12.5. Urgent events

12.5.1. Post-allogeneic transplant events

The following urgent events for Nivolumab must be reported on the appropriate Urgent Event form within **72 hours of becoming aware of the event** if they occur at any time between transplant day 0 and day 100 post-transplant in patients who receive an allogeneic stem cell transplant following nivolumab.

Event	Description	Form required	Timeframe
Grade 3 – 4 graft versus host disease	Grade 3 or 4 graft versus host disease as assessed by the modified Glucksberg criteria (see Appendix 5)	Post-allogeneic transplant urgent event form	Within 72 hours of becoming aware of event
Hyperacute graft versus host disease	Acute GVHD of any grade occurring within 14 days after stem cell infusion, and prior to neutrophil engraftment (Saliba et al 2007)	Post-allogeneic transplant urgent event form	Within 72 hours of becoming aware of event

Non-infectious febrile episodes requiring steroid therapy	Steroid responsive febrile syndrome is defined as 3 of the following major criteria or 2 major and ≥1 minor criteria: Major criteria	Post-allogeneic transplant urgent event form	Within 72 hours of becoming aware of event
(including steroid- responsive febrile syndrome)	 Non-infectious fever Rash covering >25% of body surface area Non-cardiac pulmonary oedema Minor criteria Bilirubin >17.1 µmol/L Weight gain >2.5% above baseline AST > 2 x ULN Creatinine >2 x baseline Typically occurring within 96 hours of neutrophil engraftment and responsive to corticosteroids (Spitzer 2001) Any non-infectious febrile episodes 		
	treated with steroids, occurring within 42 days post-transplant should be reported, even if the above criteria for a diagnosis of steroid-responsive febrile syndrome are not met.		
Sinusoidal obstruction syndrome (veno- occlusive disease)	2 of the following criteria occurring within 20 days after stem cell infusion: • Bilirubin >17.1 µmol/L • Hepatomegaly and/or tenderness or pain over the liver • Weight gain >20% above baseline	Post-allogeneic transplant urgent event form	Within 72 hours of becoming aware of event

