18.2.2. Analysis of secondary endpoints and secondary analyses

Survival endpoints:

Progression free survival (PFS)

PFS time will be measured from the date of the PET scan after first or second line salvage treatment (PET0) until the date of progression or death (whichever comes first). Patients who are alive and progression free will be censored at the date last seen.

Overall survival (OS)

OS time will be measured from the date of the PET scan after first or second line salvage treatment (PET0) until the date of death. Patients who are alive will be censored at the date last seen.

Analysis of PFS and OS will take place once we have 1 year follow-up for all patients. Kaplan Meier survival analyses will be used for both.

Subgroup analyses will be performed for responders and non-responders i.e. do patients with a PMR do worse than those with a CMR after nivolumab treatment. Kaplan Meier survival analysis and Cox regression may be used, although this will be dependent on the numbers of patients with a response and the numbers of events.

PFS and OS will also be analysed by further treatment i.e. did the patient go on to have an allograft or autograft, though we acknowledge that numbers will be very small so analyses will be descriptive.

CMR/PMR rates

Proportions of patients achieving CMR and PMR will also be presented.

Adverse events:

Analysis will focus on grade 3/4 adverse events. The worst grade seen per patient will be shown for each event type.

AESIs will be reported in more detail, with autoimmune events of any grade presented. All analysis will be descriptive.

Transplant related mortality and the rate of serious complications of allo SCT will presented, though again, it is likely only descriptive statistics will be used.

Other analyses:

The association between pre-nivolumab biological parameters and response to nivolumab will be investigated. As numbers will be very small mostly descriptive statistics will be used i.e. numbers and percentages will be presented for binary/categorical data and means and medians (with ranges) for continuous measurements.

We will also look at changes in TARC levels in responders and non-responders.

PET negative patients not treated with nivolumab

We will look at PFS, OS and subsequent treatments for patients who are PET negative following first or second line salvage treatment (i.e. at PET0).

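### After an allograft, colitis, dermatitis or hepatitis not proven autoimmune defaults to GVHD, but non-hyperacute grade I–II events, and any such event after day 100, have no assured form

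*Protocol*

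**What the plan says.** Five parts of the protocol bear on the same event.

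- **12.4.1, autoimmune AESIs.** The window runs from the first dose to 5 months after the last dose, and later if the investigator thinks the event is due to nivolumab. For allograft patients there is a default: "colitis, dermatitis and hepatitis occurring after transplant day 0 should be reported as graft-versus-host disease in the first instance unless otherwise proven to be" autoimmune, with a pointer to 12.5. The section also states: "confirmed autoimmune events must be reported to the CTC on an SAE report form even if the patient has received further treatment for their lymphoma".
- **12.5.1, post-allograft urgent events.** Two GVHD entries are accepted, both from day 0 to day 100. One is "Grade 3 or 4 graft versus host disease as assessed by the modified Glucksberg criteria". The other is hyperacute GVHD of any grade, within 14 days of infusion and before neutrophil engraftment.
- **12.2.1, ordinary AEs.** Recording ends "3 months post last nivolumab administration or commencement of next treatment for lymphoma (whichever is earlier").
- **12.2.2, SAEs.** For allograft patients, non-autoimmune SAE reporting ends at conditioning if that comes before 5 months. Events after further lymphoma treatment are exempt unless they are autoimmune AESIs. Exempt events are nevertheless to be entered in the CRFs.
- **18.2.2, analysis.** "AESIs will be reported in more detail, with autoimmune events of any grade presented".

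**The concern.** The default in 12.4.1 sends an event to a section that has an entry for only part of the GVHD range. A site that follows the text with an unproven, non-hyperacute grade I or II event finds no entry in 12.5.1. The ordinary AE and SAE routes closed before day 0.

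Autoimmune toxicity is the safety aspect singled out in the secondary endpoints (3.2). The safety discussion in section 2.1 names patients who go on to allogeneic transplant as a particular concern. Section 12.2.2 justifies its short SAE window by saying that the AESI rules keep immune-related events in view after new lymphoma treatment starts. For three of the eight organ AESIs (colitis, dermatitis, hepatitis), the default weakens that safeguard in these patients. At stake is whether the any-grade autoimmune presentation in 18.2.2 is complete for them.

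**Working it through.** The plan gives no figure to reproduce. The check sets the routes side by side, compares the two grading scales, and then measures the windows.

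**1. Routes for an unproven colitis, dermatitis or hepatitis event after day 0**

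| Event | 12.5.1 form | AE recording (12.2.1) | SAE report (12.2.2) |
|---|---|---|---|
| Grade 3–4, to day 100 | yes | closed | exempt, urgent event instead |
| Hyperacute, any grade | yes | closed | exempt, urgent event instead |
| Grade I–II, not hyperacute | none | closed | exempt unless an autoimmune AESI |
| Any grade, after day 100 | none | closed | exempt unless an autoimmune AESI |

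The instruction in 12.2.2 to record exempt events in the CRFs could rescue the last two rows, but 12.2.1 has ended AE recording by then. That instruction also concerns events that would otherwise be SAEs, so it does not clearly reach non-serious ones. AESIs, by contrast, are reportable whatever their seriousness.

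**2. Grade I–II does not mean mild on the CTCAE scale**

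- *Rash.* Section 8.5.1.4 gives CTCAE grade 3 as "Covering >30% body surface area; erythroderma". In Appendix 4, 25–50% of body surface is skin stage 2. With liver stage 0 and gut stage 0, reading across the rows, only grade I fits. A rash over more than 30% and up to 50% of body surface is therefore CTCAE grade 3 but Glucksberg grade I.
- *Liver.* Section 8.5.1.3 gives grade 3–4 as "AST or ALT >5xULN and /or Bilirubin >3xULN". Appendix 4 stages the liver on bilirubin alone. ALT or AST above 5 times ULN with normal bilirubin is liver stage 0 and, on its own, no Glucksberg grade.

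**3. Length of the gap**

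Inputs: the autoimmune window is 5 months, taken as 5 × 30 = 150 days (section 9.6.2 counts months 1 to 3 as 30, 60 and 90 days). The hyperacute limit is 14 days and the urgent-event limit is day 100. T, the number of days from last dose to day 0, is not in the protocol. It is assumed to be 42 to 84 days (6 to 12 weeks), with 30 and 120 as outer values.

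- Window after day 0 = 150 − T
- Days with no form for grade I–II = 150 − T − 14
- Of these, days past day 100, when no GVHD grade has a form = max(0, 150 − T − 100)

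| T (days) | After day 0 | No form, grade I–II | Of these, no form for any grade |
|---|---|---|---|
| 30 | 120 | 106 | 20 |
| 42 | 108 | 94 | 8 |
| 84 | 66 | 52 | 0 |
| 120 | 30 | 16 | 0 |

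The hyperacute route also requires that engraftment has not occurred, so 14 days is the most it can cover. These are calendar days, not expected events.

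**4. Weight of one lost event**

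With 30 treated patients, one patient whose only autoimmune event goes unrecorded lowers the any-grade proportion by 1/30 = 3.3 percentage points.

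**The case against.** The strongest reply is that the gap is narrow. The default applies only in the first instance and yields to proof. Confirmed autoimmune events still go on an SAE form after further treatment. AESI reporting starts from a confirmed diagnosis in every patient, and after an allograft GVHD is simply one more cause to exclude. There are other nets:

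- SAEs that the investigator thinks are due to nivolumab (12.2.2).
- pDILI (12.4.2).
- Steroid-treated non-infectious fever to day 42 (12.5.1).
- AE assessments scheduled at months 1 to 3, and late-toxicity assessments from month 6 (9.6.2).

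Much of this stands, and it rules out three stronger readings that a reader might infer.

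- *That all such events must be called GVHD and are lost.* The text says otherwise. Only unproven events are affected.
- *That many events are lost.* The protocol gives neither an allograft number nor an event rate, and 18.2.2 expects very small numbers by transplant type.
- *That the GVHD rate is also biased down.* The endpoint in 3.2 is grade 3–4 or hyperacute GVHD, so leaving out other grade I–II events follows its definition.

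The nets do not close the gap, however. If the default label generates no form, the sponsor has nothing to query or reclassify later. The related-SAE route sits uneasily with the 12.2.2 exemption, whose only stated exception for events after further treatment is an autoimmune AESI, and it does not cover non-serious events. pDILI requires bilirubin above 2 times ULN, and the febrile route requires fever. The assessments at months 1 to 3 remain scheduled, but 12.2.1 has closed recording. Those from month 6 fall after the window and ask about nivolumab toxicity, not events labelled GVHD.

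**Conclusion.** The point holds in limited form. Sections 12.2.1, 12.2.2, 12.4.1 and 12.5.1 do not fit together. Inside the 5-month autoimmune window, two kinds of unproven colitis, dermatitis or hepatitis have no assured form: non-hyperacute events of Glucksberg grade I–II (or no grade), and events of any grade after day 100. Some of these are CTCAE grade 3.

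The uncovered stretch for grade I–II is 52 to 94 days if day 0 falls 6 to 12 weeks after the last dose, and 16 to 106 days for an interval of 30 to 120 days. Both intervals are assumptions. The after-day-100 part arises only if day 0 comes less than 50 days after the last dose.

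The number of events is unknown and probably small. The possible bias is downward and concerns the autoimmune toxicity count only, to the extent that unproven events are in truth due to nivolumab. With about 30 treated patients and descriptive reporting, even one or two unseen events would matter, so the change is worth making.

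**What to change.** Reconcile 12.2.1, 12.2.2, 12.4.1 and 12.5.1 so that every colitis, dermatitis or hepatitis event after day 0 and within 5 months of the last dose is captured, whatever its Glucksberg grade and including after day 100. The existing post-allogeneic form or the follow-up CRF would serve. Grade I–II events need to be recorded, not necessarily within 72 hours. For each event, collect organ stage, CTCAE grade and attribution (GVHD, autoimmune, undetermined). State in 12.2.1 that this recording continues after the AE window closes.

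In 18.2.2, present autoimmune events with and without those attributed to GVHD or undetermined. While 12.5.1 is open, correct its cross-reference: the Glucksberg criteria are in Appendix 4, not Appendix 5.

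The cost is protocol wording, a few fields on an existing form, and some extra entries in a small subgroup. No treatment rule changes.

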12.4.2 Potential Drug Induced Liver Injury (pDILI)

All occurrences of potential DILIs, meeting the defined criteria below, must be reported as SAEs.

Potential drug induced liver injuries should be reported from the first administration of nivolumab until five months post-treatment (or after this date if the investigator feels the event is related to nivolumab).

Event	Description	Form required	Timeframe
Potential drug induced liver injury (pDILI)	AST or ALT >3 x ULN and Total bilirubin >2 x ULN, without initial findings of cholestasis (elevated serum alkaline phosphatase)	SAE report	Within 24 hours of diagnosis
	and No other immediately apparent causes of transaminase elevation and hyperbilirubinemia, including, but not limited to, viral hepatitis, pre-existing chronic or acute liver disease, or the administration of other drug(s) known to be hepatotoxic.		

Cases of pDILI must be reported on the trial-specific SAE report by fax or email: [contact]

Email: [contact]

12.4.3. Overdoses

Any overdoses of nivolumab, must be reported as both an SAE and an incident within 24 hours of the overdose occurring, regardless of whether the patient experiences any adverse events as a result of the overdose. Examples of potential overdoses are listed in the table below. If there is uncertainty about whether a patient has been overdosed, please contact the ANIMATE study team to discuss ([contact]).

Any adverse events occurring in patients who have received an overdose should be reported as serious events within the SAE report.

Event	Examples	Forms required	Timeframe
Overdose	 Administration of a nivolumab dose in excess of 240mg at any individual dosing episode Administration of a cumulative nivolumab dose in excess of 1920mg (240mg x 8 doses) 	SAE reportIncident report	Within 24 hours of overdose occurring

Overdoses must be reported by sending both the trial-specific SAE report and incident report by fax or email:

[contact]

Email: [contact]

